**1.3.2. Part B Study Schedule (Repeat Dose Cohort)**

Procedure	Screening	Inpatient Visit 1			Outpatient Follow-up Visits a					Inpatient Visit 2			Outpatient Follow-up Visits a										ET
													Post-Dose					Monitoring Extention b					
Week																							
CCI	CCI	CCI	CCI	CCI	CCI	CCI	CCI	CCI	CCI	CCI	CCI	CCI	CCI	CCI	CCI	CCI	CCI	CCI	CCI	CCI	CCI		
Informed Consent	X																						
Demographics	X																						
Medical history	X	X																					
Review/confirm I/E criteria	X	X d																					
Randomization		X																					
Admit to CRU		X								X													
Discharge from CRU e				X							X												
Administer study intervention f			X							X													
Physical examination g	X	X	X	X	X	X	X	X	X	X		X	X	X	X	X	X	CCI	X		X		
Height	X																						
Weight h	X	X							X						X			CCI			X		
COVID-19 PCR test i	X	X							X														
Pregnancy test j	X	X							X									CCI	X		X		
FSH k	X																						
Hepatic serologies l	X																						
Urine drug screen and ethanol	X	X																					
Urinalysis	X	X			X	X						X	X										
Safety laboratory tests	X		P	X	X	X	X	X	X		P	X	X	X	X	X	X	CCI	X		X		
Body Temperature m	X		P								P										X		
Vital signs -- PR/BP/RR	X		CCI	CCI	X	X	X	X	X	X	CCI	CCI	X	X	X	X	X	CCI	X		X		
12-lead ECG n, v	X		CCI	CCI	X						CCI	CCI	X					CCI	X		X		
Transient Elastography o	X																						
MRI-PDFF and MRI p	X									X							X						
Plasma PK samples p			CCI	CCI	CCI	CCI	CCI	CCI	CCI		CCI	CCI	CCI	CCI	CCI	CCI	CCI	CCI		CCI			
Lipid panel (fasting) q	CCI		CCI	CCI		CCI	CCI		CCI		CCI	CCI	CCI	CCI	CCI	CCI	CCI	CCI		CCI			
ApoB (fasting)			CCI	CCI		CCI	CCI		CCI		CCI	CCI	CCI	CCI	CCI	CCI	CCI	CCI		CCI			
Stored samples (fasting)			CCI	CCI		CCI	CCI		CCI		CCI	CCI	CCI	CCI	CCI	CCI	CCI	CCI		CCI			

Procedure	Screening	Inpatient Visit 1		Outpatient Follow-up Visits a					Inpatient Visit 2			Outpatient Follow-up Visits a										E
												Post-Dose						Monitoring Extention b				
Week																						
Day																						
ISR assessments			Following spontaneous report from participant, complete ISR CRF and Pain VAS assessment																			
Immunogenicity																						
AE/concomitant medications	X	X	X	X	X	X	X	X	X	X	X	X	X	X	X	X	X	X	X	X		
HbA1c	X		P								P							D260		X		
PCSK9																						
CCI	X		P			X		X			P			X			X	D176, 260		X		

Abbreviations: AE = adverse event; Apo = apolipoprotein; BP = blood pressure; CAP = controlled attenuation parameter; CCI = COVID-19; COVID-19 = Coronavirus disease 2019; CRF = case report form; CRU = clinical research unit; CCI = COVID-19; D = day; ECG = electrocardiogram; CCI = COVID-19; ET = early termination; CCI = COVID-19; h = hour(s), FSH = follicle-stimulating hormone; HbA1c = glycated hemoglobin; HCV = hepatitis C virus; HDL-C = high-density lipoprotein cholesterol; I/E = inclusion/exclusion; ISR = injection-site reaction; LDL-C = low-density lipoprotein cholesterol; CCI = COVID-19; min = minutes; MRI-PDFF = magnetic resonance imaging proton density fat fraction; CCI = COVID-19; P = predose; PCR = polymerase chain reaction; PCSK9 = proprotein convertase subtilisin/kexin type 9; PD = pharmacodynamics; PK = pharmacokinetics; PR = pulse rate; CCI = COVID-19; PR = pulse rate; RR = respiration rate; SC = subcutaneous; TEAE = treatment-emergent AE; TG = triglyceride; VAS = visual analog score; VLDL-C = very low-density lipoprotein cholesterol.

- All follow-up visits should take place in the morning after an overnight fast of at minimum 8 hours. Water is permitted ad libitum during the fasting period.
- After Day 260, once any treatment related AEs are resolved and PCSK9 levels return to at least CCI% of baseline, the Monitoring Extension visits may be discontinued. The final visit of a participant who completes the study will be the first scheduled Monitoring Extension visit after they report no ongoing AEs, and after PCSK9 levels have returned to at least CCI% of baseline in a blood sample collected at one of the preceding visits. At the participant's final visit, they will receive the assessments performed at ET, except for the collection of a blood sample for PCSK9 assessment.
- Outpatient follow-up visits on Days CCI and CCI will be conducted through a remote telehealth visit assessing AE/concomitant medications.
- On Day -1 prior to randomization review AEs, concomitant medications, and compliance to protocol restrictions.
- Discharge from CRU after all assessments have been completed.
- All doses of study intervention will be administered SC in the morning after an overnight fast of at minimum 8 hours. Water is permitted ad libitum during the fasting period.
- Complete physical examination at screening; symptom-directed examinations at all other visits.
- Body weight is measured at any time before breakfast.
- A COVID-19 PCR test will be performed at Screening. and on Days -1 and 84 upon admission to CRU. If test results are positive for the virus the participant will be excluded from the study.
- A serum pregnancy will be performed at screening. Urine pregnancy tests will be performed at all other visits. If a urine test result is positive, the result will be confirmed with a serum test.
- A serum FSH test should be performed in women at screening to confirm postmenopausal status.

- l If the HCV antibody test is positive, it must be followed by an HCV RNA test. Participants who are positive for HCV antibody and negative for HCV RNA may be enrolled. See Exclusion Criterion #8, Section 5.2.
- m Temperature also measured at any additional time points as clinically indicated.
- n Single 12-lead ECG at screening, safety follow-up and/ ET visit. Three triplicate 12-lead ECGs at pre-dose 2 minutes apart to establish baseline. Triplicate 12-lead ECGs at all other scheduled times. The actual day and time must be documented in the CRF.
- o Participants must meet the CAP inclusion criteria prior to MRI assessment (Section 5.1). If CAP has been completed within 4 weeks before screening, this test does not need to be repeated.
- p Recording times identified with an X may be obtained at any time within the scheduled days; the exact date and time of recording must be recorded in the CRF.
- q Lipid panel: TG, total cholesterol, LDL-C, VLDL-C (calculated), HDL-C, non-HDL-C (calculated).
- r CCI [REDACTED]

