- i A COVID-19 PCR test will be performed at Screening and on Day -1 prior to dosing. If test results are positive for the virus the participant will be excluded from the study.
- j A serum pregnancy will be performed at screening. Urine pregnancy tests may be performed at all other visits. If a urine test result is positive, the result will be confirmed with a serum test.
- k A serum FSH test will be performed in women at screening to confirm postmenopausal status.
- l If the HCV antibody test is positive, it must be followed by an HCV RNA test. Participants who are positive for HCV antibody and negative for HCV RNA may be enrolled. See Exclusion Criterion #8, Section 5.2.
- m Single 12-lead ECG at screening, safety follow-up and ET visit. Three triplicate 12-lead ECGs at pre-dose 2 minutes apart to establish baseline. Triplicate 12-lead ECGs at all other scheduled times. The actual day and time must be documented in the CRF.
- n PK samples identified with an X may be obtained at any time within the scheduled days; the exact date and time of blood sample collection must be recorded in the CRF.
- o Lipid panel: TG, total cholesterol, LDL-C (PUC), VLDL-C (calculated), HDL-C, non-HDL-C (calculated).

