## 5. Study Population

Prospective approval of protocol deviations to recruitment and enrollment criteria, also known as protocol waivers or exemptions, are not permitted.

The eligibility of participants for enrollment in the study will be based on the results of screening medical history, physical examination, vital signs, clinical laboratory tests, and ECG. The nature of any conditions present at the time of the physical examination and any preexisting conditions will be documented.

The inclusion and exclusion criteria used to determine eligibility should be applied at screening (Days -28 to -1), and prior to randomization when participants arrive at the clinic on Day -1 only.

Screening will occur up to **CC1** days prior to enrollment. Participants who are not enrolled within **CC1** days of screening may undergo additional medical assessment, clinical measurements, or both to confirm their eligibility. In such instances, the following screening tests and procedures will be repeated: medical assessment, vital signs, clinical laboratory tests, and ECG.

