***Participants in Part A and B:***

1. Sponsor (Eli Lilly and Company) employees, contract research organization (CRO) employees, Investigator or site personnel directly affiliated with this study or their immediate families (spouse, parent, child, or sibling, whether biological or legally adopted).
2. Treatment with another investigational drug, biological agent, or device within 30 days of Screening Visit or 5 half-lives of investigational agent, whichever is longer.
3. History or presence of medical illness including, but not limited to, any cardiovascular, thromboembolism or bleeding disorder, hepatic, respiratory, hematological, endocrine, immune, psychiatric, or neurological disease, convulsions, or any clinically significant laboratory abnormality that, in the judgment of the Investigator, indicate a medical problem that would preclude study participation.
4. Supine heart rate greater than CCI bpm. A repeat measure is permitted.
5. Uncontrolled hypertension with a resting blood pressure  $\geq 160$  mmHg systolic or  $\geq 100$  mmHg diastolic at visit 1; a repeat assessment is permitted.
6. Have had any of the following within the past CCI days prior to screening: myocardial infarction, unstable angina, coronary artery bypass graft, percutaneous coronary intervention (diagnostic angiograms are permitted), transient ischemic attack, cerebrovascular accident, hospitalization due to heart failure.
7. Have New York Heart Association functional Classification III-IV congestive heart failure.
8. Current infection with Coronavirus disease 2019 (COVID-19).
9. Current infection with hepatitis B virus (HBV), that is, positive for hepatitis B surface antigen (HBsAg) and/or polymerase chain reaction (PCR) positive for HBV deoxyribonucleic acid (DNA).

10. Hepatitis C as defined by presence of hepatitis C virus (HCV) RNA. Participants treated for hepatitis C (and diagnosed as cured) must have a RNA test at screening and be RNA negative for at least 2 years prior to screening to be eligible for the study.
11. Human immunodeficiency virus (HIV) infection.
12. Average weekly alcohol intake that exceeds 21 units per week (males) or 14 units per week (females), or are unwilling to stop alcohol consumption from 48 hours prior to admission to and while resident at the CRU (1 unit = 12 oz or 360 mL of beer; 5 oz or 150 mL of wine; 1.5 oz or 45 mL of distilled spirits).

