## **7. Discontinuation of Study Intervention and Participant Discontinuation/Withdrawal**

Discontinuation of specific sites or of the study as a whole are handled as part of Appendix 1 (Section 10.1).

Participants discontinuing from study intervention prematurely for any reason should complete AE and other follow-up procedures per the SoA (Section 1.3) of this protocol.

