### **7.1. Discontinuation of Study Intervention**

It may be necessary for a participant to permanently discontinue study intervention (applies only to Part B). If study intervention is permanently discontinued, the participant will remain in the study to complete procedures for an early termination visit and post-treatment follow-up, if applicable, as shown in the SoA (Section 1.3).

In Part B, prior to the repeat dose, all available safety data will be reviewed. Any clinically significant findings that may determine if further dosing should be discontinued will be determined by the Investigator in consultation with the Sponsor. A second dose will not be administered if the study participant experienced a hypersensitivity reaction after receiving the first dose in Part B of the study.

A participant should be permanently discontinued from study intervention if:

- The participant becomes pregnant during the study
- The participant decides to discontinue study intervention
- The Investigator decides that the participant should be discontinued due to AEs (the participant will be followed until the AE resolves)
- The participant has a SAE considered related to study treatment.

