
Urinalysis:
 
 
Specific gravity
 
pH
 
Protein
 
Glucose
 
Ketones
 
Bilirubin
 
Urobilinogen
 
Blood
 
Nitrite
 
 
CCI [REDACTED]
	
Lipids:
 
 
Total cholesterol
 
Triglycerides (TG)
 
Low-density lipoprotein (LDL)
 
High-density lipoprotein (HDL)
 
Very low-density lipoprotein (VLDL)
 
CCI [REDACTED]
 
 
PCSK9 (Proprotein convertase subtilisin/kexin type 9) and ApoB
 
Ethanol testinga,b
 
Urine drug screena,b
 
Hepatic serologies:a
 
 
Hepatitis B surface antigen (HBsAg)
 
HBV DNA
 
Hepatitis C antibody
 
HCV RNA
 
 
Stored sample
 
 
Human immunodeficiency virus (HIV)a
 
COVID-19 PCR testc
 
Pregnancy testd
 
Follicle-stimulating hormone (FSH)e
 
Thyroid-stimulating hormone (TSH)a
 

---

FIB-4 formula = Age (years)  $\times$  AST (IU/L) / {platelet count ( $10^9$ /L)  $\times$  ALT (IU/L)1/2}

- a Performed at screening only.
- b Urine drug screen and ethanol level must be repeated prior to admission to the clinical research unit (CRU) and at other times indicated in the Schedule of Activities (SoA) in Section 1.3.
- c A COVID-19 PCR test will be performed at Screening, and on Day 1 prior to dosing. If test results are positive for the virus the participant will be excluded from the study.
- d Serum pregnancy test at screening; urine pregnancy test may be performed at all other timepoints and at other times indicated in Schedule of Activities (SoA )
- e A serum FSH test should be performed in women at screening to confirm postmenopausal status if applicable.
- f CCI [REDACTED]

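### The Part B COVID-19 footnote excludes a participant for a positive Day 84 test, after dose 1, which is inconsistent with the Section 7 follow-up rule

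*Protocol*

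**What the plan says.** The footnote to the COVID-19 PCR row of the Part B schedule (Protocol Section 1.3.2) calls for a screening test and then for two more, with one consequence for all of them: "on Days -1 and 84 upon admission to CRU. If test results are positive for the virus the participant will be excluded from the study". Day 84 is the second admission to the research unit, made for dose 2.

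The protocol treats current COVID-19 infection as an entry matter: it is exclusion criterion 8 in Section 5.2. Section 5 applies the entry criteria at screening and "prior to randomization when participants arrive at the clinic on Day -1 only".

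For people who stop treatment, the opening of Section 7 says: "Participants discontinuing from study intervention prematurely for any reason should complete AE and other follow-up procedures per the SoA". Section 7.1, which concerns Part B only, adds that "the participant will remain in the study to complete procedures for an early termination visit and post-treatment follow-up, if applicable, as shown in the SoA". COVID-19 is not listed as a reason for stopping study intervention (Section 7.1) or for withdrawal (Section 7.2).

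**The concern.** At screening or Day -1, excluding an infected person costs no safety information, because nothing has been given. At Day 84 the same word removes someone who has been exposed to a first-in-human product. The primary endpoints are AEs and SAEs. Section 4.3.4 expects the effect of a single dose to last well beyond the drug's time in plasma, with return to baseline possibly taking months. Participants who complete the study must also show PCSK9 recovery before their last visit (Section 1.3.2).

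If exclusion were taken to end participation at Day 84, that recovery check could be lost, along with later safety visits and MRI-PDFF scans. Under Section 9.3.2, an AE arising after an early termination visit would be analysed only if judged at least possibly related to the drug.

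**Working it through.** The plan gives no figure to reproduce, so the check is mainly a comparison of texts, followed by a bound.

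1. **Status at Day 84.** The Synopsis has Part B participants randomised at the start of Cohort 7, first dosed on Day 1, and readmitted later for dose 2. The day of readmission is masked elsewhere and the schedule table is hard to read, so Day 84 rests on the footnote's own words. On those words, everyone tested at Day 84 is already randomised and dosed.

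2. **Entry rules.** Section 5 stops applying the entry criteria at Day -1. The schedule row "Review/confirm I/E criteria" is marked only at Screening and Inpatient Visit 1. Nothing else in the protocol makes Day 84 an eligibility decision.

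3. **Parallel sentences.** Part A footnote i reads "A COVID-19 PCR test will be performed at Screening and on Day -1 prior to dosing". Appendix 2 footnote c reads "A COVID-19 PCR test will be performed at Screening, and on Day 1 prior to dosing". Both carry the same exclusion sentence, but each lists only tests before dosing. The Part B footnote adds a post-dose day under that sentence and leaves the consequence unchanged.

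4. **What happens to follow-up.**
   - Section 7: stopping intervention for any reason leads to follow-up according to the schedule.
   - Section 7.1: the participant stays in the study, and post-treatment follow-up is done where applicable.
   - Section 7.2: on leaving the study, an early discontinuation visit is done if possible and post-treatment follow-up where applicable. Anyone still on intervention is taken off it at that point.
   - The footnote mentions none of these routes. It also sits inside the schedule to which Section 7 refers, so a site cannot tell which instruction governs.

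5. **Comparison with hypersensitivity.** After a hypersensitivity reaction to dose 1, Section 7.1 withholds dose 2 and Section 8.2.8 continues follow-up on schedule. A positive swab, which need not have anything to do with the drug, gets the harsher rule as written.

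6. **Bound on what could be lost.** Monitoring Extension visits may stop only after Day 260 (Section 1.3.2).
   - Upper bound: 260 − 84 = 176 days; 176/7 = 25.1 weeks; 176/260 = 67.7% of the minimum period. This assumes no follow-up at all after the positive test.
   - Lower bound: 0 days, if Section 7 is applied in full.
   - Exposure: Arms 1 and 2 in Table 4.2 give 11 + 11 = 22 of 44 participants with active drug at dose 1.

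**The case against.** A PCR test on readmission to a residential unit is ordinary infection control. The footnote does not cite criterion 8, and no eligibility review is marked at Inpatient Visit 2. It can therefore be read as an on-study stopping rule with a badly chosen verb. That stands. A reader might infer that the footnote directly contradicts Section 5, but the documents do not go that far: testing at Day 84 is compatible with Section 5, and only the entry-stage consequence is out of place.

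Follow-up may also survive. Section 7.2 takes a participant who leaves the study off intervention, and the opening of Section 7 then asks for follow-up whatever the reason. As far as the table can be read, the early termination visit includes safety laboratory tests, vital signs and ECG, and the Monitoring Extension footnote implies a PCSK9 sample as well. Under Section 8.3, AEs already open are followed to resolution or stabilisation, and Section 8.3.1 provides for reporting of possibly related SAEs after participation ends. This stands in large part. A reader might infer that 176 days of follow-up are certainly lost, and the documents do not support that.

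What remains is a mandatory instruction that does not match the protocol's own follow-up rule. Infection control justifies keeping the person out of the unit and not dosing them, but not ending their participation. The investigator's power to withdraw someone for safety (Section 7.2) is discretionary, whereas the footnote is automatic.

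Finally, the Part B text was provisional. The protocol was to be amended before Part B, although Section 6.3.2 describes that amendment in terms of dose level and frequency.

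**Conclusion.** The point holds as an inconsistency of wording with a possible safety-follow-up consequence. The footnote applies entry-stage language to a randomised, dosed participant and does not agree with Section 7. Per affected participant the loss is between 0 and 176 scheduled days, depending on whether a site follows the footnote literally or reads Sections 7 and 7.2 together. The documents do not settle which.

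Two further inferences should be resisted. The documents give no COVID-19 positivity rate, so any expected number of exclusions, or chance of at least one, would only restate an assumed input; none is offered. Nor is there ground for claiming bias between arms: the same rule covers all three arms under blinding.

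Importance is minor. The SAP (Sections 1 and 2) states that the study was discontinued after Cohort 5 and would not proceed to Part B, so no participant, analysis or result is affected. The text would matter if this schedule were reused in a repeat-dose protocol.

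**What to change.** Limit exclusion to a positive test at Screening or Day -1. For a positive Day 84 test, state that:

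- the participant is not admitted or dosed while infected;
- dose 2 is decided at the safety review that Section 7.1 already requires before the repeat dose;
- the participant stays in scheduled safety, PCSK9 and MRI-PDFF follow-up under Section 7, with on-site assessments rescheduled;
- AE contacts may be made remotely while the participant is infectious.

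The cost is a few sentences plus one short new provision. The remote contacts do need that provision: the telehealth visits in Section 1.3.2 fall on fixed days, and the remote visits in Appendix 6 are temporary measures for exceptional circumstances that need the sponsor's written approval. The schedule appears to place the second MRI-PDFF scan at Inpatient Visit 2, so that scan may have to move.

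The downside is some rescheduled visits and a second dose that may be delayed or missed. In Arm 1, the only two-dose arm, one missed second dose is 1/11 = 9.1% of the arm. Exclusion as now written would lose that dose in any case, and possibly the later follow-up with it.

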## 2. Introduction

LY3885125 CCI is a novel Dicer-substrate small interfering ribonucleic acid (DsiRNA) conjugated to N-acetylgalactosamine CCI designed to specifically knock down sterol regulatory element binding protein (SREBP) cleavage activating protein (SCAP) messenger ribonucleic acid (mRNA) in the liver. SCAP regulates the activation of SREBPs, which are transcription factors that govern *de novo* lipogenesis, cholesterol biosynthesis, and metabolism pathways. LY3885125 is being developed to reduce hepatic SCAP mRNA levels and thereby reduce SCAP protein expression. CCI

### 2.1. Study Rationale

CCI

Given these effects, there is potential for LY3885125 as a treatment for dyslipidemia and nonalcoholic fatty liver disease (NAFLD).

Study J4N-MC-YFAA is a first-in-human (FIH) placebo-controlled study, which will evaluate the safety, tolerability, pharmacokinetics (PK), and pharmacodynamics (PD) of single ascending subcutaneous (SC) doses of LY3885125 in participants with dyslipidemia (Part A), and of repeated SC doses of LY3885125 in participants with NAFLD and CCI (Part B). In Part A, response to LY3885125 will be assessed based on changes in circulating proprotein convertase subtilisin/kexin type 9 (PCSK9) concentration. In Part B the effect of LY3885125 compared with placebo on liver fat content (LFC) will be evaluated through changes in magnetic resonance imaging proton density fat fraction (MRI PDFF).

